**BRACHY-CHOR-001** 

#### Introduction

This Statistical Analysis Plan (SAP) details the statistical methodology to be used in analyzing trial data and outlines the statistical programming specifications, tables, figures, and listings. It describes the variables and populations, anticipated data transformations and manipulations, and other details of the analyses not provided in the trial protocol.

This statistical plan will be followed completely for the analysis of data derived from the clinical trial. If any additional analyses are included in the clinical study report (CSR), they will be clearly described as additional, unplanned analyses.

The analyses described within are based on the final clinical trial protocol: *A Phase 2 Trial of BN-Brachyury and Radiation Therapy in Patients with Advanced Chordoma, Version 4.0* dated 22-Aug-2019. The current SAP includes all analyses that will be performed for the final CSR.

The SAP is archived with other pertinent trial documentation as noted in Bavarian Nordic (BN) SOP BN0003973.

**BRACHY-CHOR-001** 

Overall Treatment Period: All data collected from the first vaccination of trial treatment through the last trial visit (regardless of completion status) will be considered part of the overall treatment period. A final visit is planned for approximately 30 days after the last treatment visit. Specifically, the overall treatment period will consist of the pre-radiation vaccination period, radiation therapy period, post-radiation vaccination period 1 and post-radiation vaccination period 2, which are defined below.

**Pre-Radiation Vaccination Period**: The time from the date of first vaccination of MVA-BN-Brachyury to the day prior to the start of radiation therapy. Subjects should have received 2 doses of MVA-BN-Brachyury and 1 dose of fowlpox (FPV)-Brachyury during this period.

**BN-Brachyury:** Term that refers to both MVA-BN-Brachyury and FPV-Brachyury trial vaccines when used together in a prime-boost regimen.

**Radiation Therapy Period**: from the start date of radiation therapy to the day prior to resuming FPV-Brachyury injections.

**Post-Radiation Vaccination Period 1**: The time from the date of restart of FPV-Brachyury injections after radiation therapy to the day prior to the scheduled FPV-Brachyury injection at the End Radiation + 26 weeks visit. FPV-Brachyury will be administered every 4 weeks during this period.

**Post-Radiation Vaccination Period 2**: The time from the date of the FPV-Brachyury injection at the End Radiation + 26 weeks visit to the last scheduled trial visit (i.e., last injection of FPV-Brachyury + approximately 30 days). FPV-Brachyury will be administered every 12 weeks during this period.

**Treatment Emergent Adverse Events**: An AE with an onset on or after initiation of trial treatment, or an AE present at initiation of trial treatment that worsens (*i.e.*, increase in severity: On-Trial Grade > Baseline Grade) as determined by the investigator will be considered a treatment-emergent adverse event (TEAE). TEAEs are collected through the last scheduled visit (approximately 30 days after the last dose of trial product).

Serious Adverse Events (SAEs) and AEs of Special Interest (AESIs): SAEs and AESIs that occur on or after initiation of trial treatment through 30 days after the last dose of trial product are considered as TEAEs. SAEs and AESIs will be followed until resolution.

Modified Response Evaluation Criteria in Solid Tumors (mRECIST): Standard Response Evaluation Criteria in Solid Tumors (RECIST) Version 1.1 to be used only for radiographic assessment of the irradiated tumor(s) (target lesions). Non-irradiated tumors (non-target lesions) will not be part of the mRECIST assessment. Refer to Section 3.5.3.2 for additional details.

**Response:** Response for the primary analysis will be determined using mRECIST or Immune-Related Response Criteria (irRC), in which only target tumors receiving adequate radiotherapy will be considered for RECIST assessment and primary endpoint analysis. Progression of non-

BRACHY-CHOR-001

target lesions will be assessed as exploratory analyses based on standard RECIST 1.1 for this trial. Refer to Section 3.5.3.2 for additional details.

**Progressive Disease (PD)**: Advancement of disease as defined by target tumor enlargement from nadir using mRECIST or irRC. Progression of non-target lesions will not be considered as disease progression for the primary endpoint analysis of this trial.

**Target Lesions:** Only tumors that are measurable and have received adequate radiotherapy will be considered target lesions for determination of response. All other tumors will be considered non-target lesions.

**Objective Response (OR)**: A subject achieving Complete Response (CR) or Partial Response (PR) per mRECIST or irRC.

Objective Response Rate (ORR): The proportion of subjects meeting the criteria for OR.

**Duration of Response**: From the time that criteria are first met for CR or PR (whichever is first recorded) until the first date that recurrent or progressive disease is objectively documented. The smallest target-tumor measurements on trial (i.e., nadir tumor load) will be used as reference for progressive disease.

**Progression Free Survival (PFS)**: The time interval from the date of first trial vaccination to objective tumor progression, or death from any cause occurring prior to tumor progression. The rate of PFS at a fixed time point is defined as the proportion of subjects who have not experienced objective progression or death from the date of first trial vaccination to the fixed time point of interest.

**Brief Pain Inventory-Short Form (BPI-SF)**: A questionnaire to evaluate the severity of a subject's pain and the impact of this pain on the subject's daily functioning.

02 November, 2021

BRACHY-CHOR-001

#### 1 Trial Overview

## 1.1 Trial Description

This is a single-arm phase 2 clinical trial using a Simon two-stage optimal design (Simon, 1989). The goal is to demonstrate that BN-Brachyury plus radiation therapy can induce objective radiographic responses in subjects. In stage 1, a minimum threshold of activity will be needed to proceed to stage 2.

[figure not shown]
Stage 1: Enroll 10 subjects. If objective response (OR) is not achieved in any subjects, the trial will be stopped for lack of activity. If OR is achieved in ≥1 subject, the trial will proceed to stage 2. If any subject is not evaluable for the primary endpoint, the subject may be replaced.

Stage 2: Enroll an additional 19 subjects for a total of 29 subjects. If any subject is not evaluable for the primary endpoint, replacement subjects may be enrolled until a total of 29 subjects are evaluable for the primary endpoint.

Subjects will be treated with two priming doses of MVA-BN-Brachyury (Doses 1 and 2) and one dose of FPV-Brachyury (Dose 3) prior to initiation of radiotherapy. Radiotherapy will begin at least 2 weeks and not more than 4 weeks after first administration of FPV-Brachyury (Dose 3). At least 2 weeks following completion of radiotherapy (or upon resolution of any reversible AEs related to radiotherapy), the subject will resume vaccination with FPV-Brachyury and proceed to ongoing booster doses with FPV-Brachyury through approximately 2 years beyond completion of radiotherapy. A final visit will occur 30 days after the last treatment visit. Refer to Figure 1 for a summary of the trial vaccine schedule.

**BRACHY-CHOR-001** 

Figure 1 Trial Vaccination Schedule

## 1.2 Objectives

## 1.2.1 Primary Objective:

To determine if the combination of BN-Brachyury administered with radiotherapy will result in a clinically meaningful ORR when compared with historical control.

## 1.2.2 Secondary Objectives:

- To confirm the safety profile of BN-Brachyury plus radiation therapy
- PFS by mRECIST 1.1 criterion
- Improvement in clinical symptoms as measured by the Brief Pain Inventory-Short Form (BPI-SF) pain assessment

## 1.2.3 Exploratory Objectives:

- To evaluate the differences in clinical outcome measures by location of primary tumor (Sacral vs. Mobile Spine vs. Clival)
- To measure AE profile by location of primary tumor
- To evaluate other clinical endpoints that might be indicative of clinical benefit:
  - ORR by standard RECIST 1.1

- o PFS by other criteria, including Choi, volumetric, and standard RECIST 1.1
- To evaluate changes in immune and tumor related biomarkers of pre- versus post-baseline samples
  - o Peripheral blood mononuclear cells (PBMC)
    - Brachyury and other tumor-associated antigen (TAA) specific T-cell activation
    - Immune cell subset quantification and characterization
  - Serum
- Analysis for soluble factors associated to immune response, e.g., antibodies or cytokines

## 1.3 Trial Population

The population proposed for inclusion in this trial are male and female subjects at least 12 years old with advanced chordoma who are planning to be treated with radiotherapy to at least one lesion. In an effort to demonstrate clinical activity in the population most likely to be eligible for this treatment, adolescents have been included.

#### 1.4 Inclusion/Exclusion Criteria

The full list of inclusion and exclusion criteria for the trial can be found in the synopsis of the trial protocol.

## 1.5 Endpoints

#### **Primary endpoints:**

• ORR anytime within 12 months post-completion of radiation on target lesion(s) based on mRECIST 1.1 or irRC. Refer to Section 3.5.3.2 for the modified response criteria.

#### **Secondary efficacy endpoints:**

- PFS by mRECIST 1.1 or irRC on target lesion(s)
- Improvement in clinical symptoms measured by the BPI-SF

#### **Safety endpoints:**

- Injection site reactions
- Other AEs
- Clinically significant shifts in chemistry and hematology laboratory values

BRACHY-CHOR-001

#### **Exploratory endpoints:**

- ORR anytime post completion of radiation on all lesions by standard RECIST 1.1
- ORR anytime within 12 months post completion of radiation on target lesion(s) based on Choi criteria (Choi et al., 2007) and volumetric criteria (Fenerty et al., 2016)
- PFS based on all lesions by standard RECIST 1.1
- PFS based on target lesion(s) by other criteria:
  - o Choi criteria (Choi et al., 2007)
  - o Volumetric (Fenerty et al., 2016)
- PBMC samples: T-cell response to BN-Brachyury

## 2 Trial Design

The schedules of events can be found in the Appendices.

#### 3 Statistical Methods

## 3.1 Planned Sample Size

The null hypothesis that the true ORR anytime within 12 months after completion of radiation is 5% will be tested based on a one-sided alternative. In the first stage, 10 subjects will be accrued. If there are 0 responders in these 10 subjects, the trial will be terminated. If there is at least 1 responder in these 10 subjects, 19 additional subjects will be accrued for a total of 29 subjects. The null hypothesis will be rejected if 4 or more responses are observed in 29 subjects. This design retains a one-sided type I error rate of  $\leq 0.05$  and achieves 80% power when the true response rate is 20%.

The optimal design minimizes the expected sample size under the null hypothesis while satisfying the type I error and power constraint. With the above design, the probability of early termination is 60% and the expected sample size is 17.6 when the true response rate is 5% (under the null hypothesis).

## 3.2 Analysis Sets

For the statistical analysis, there are two analysis sets: the Evaluable Analysis Set (EAS) and the Full Analysis Set (FAS).

The EAS consists of all subjects who have completed the following:

- Two prime doses of MVA-BN-Brachyury, and
- One booster dose of FPV-Brachyury prior to radiation, and

**BRACHY-CHOR-001** 

- Completed radiation therapy, and
- At least 3 out of 4 booster doses of FPV-Brachyury in 14 weeks after radiation, and
- Have both baseline (defined as measurement prior to first prime dose of MVA-BN-Brachyury), and at least one post-baseline computed tomography (CT) or magnetic resonance imaging (MRI) scan for objective tumor evaluation.

The primary analysis population for ORR anytime within 12 months after completion of radiation and secondary efficacy endpoints is the EAS. Subjects who failed to meet the evaluable criteria will be replaced to retain the statistical power unless four or more responses have been observed or the number of responders will still be less than four even if all replacement subjects would be responders. If there are more than 10 evaluable subjects at the end of stage 1 analysis or more than 29 evaluable subjects at the end of stage 2 analysis, primary evaluation will be based on the first 10 accrued or first 29 accrued evaluable subjects. Sensitivity analyses will include all evaluable subjects if applicable.

The FAS consists of all subjects who have enrolled and received any dose of MVA-BN-Brachyury or FPV-Brachyury. This is the primary analysis set for safety and immune response, and the secondary analysis set for efficacy.

## 3.3 Subgroups

Location of primary tumor: Sacral, Mobile Spine, or Clival

Histologic subtype: Classic, Chondroid

## 3.4 Data Conventions and Handling of Missing Data

## 3.4.1 Missing or Partial Dates

All data will be listed as captured in the electronic case report form (eCRF); however, it may be necessary to impute incomplete dates to correctly assign events to a period or to calculate durations.

For prior and concomitant medications, AEs, and cancer history dates, the following rules will apply:

BRACHY-CHOR-001

BN-Brachyury-TRICOM Vaccine

02 November, 2021

Missing	Rule for Start Date	Rule for End Date	Imputation Flag			
Day	First of Month	Last of Month	D			
Month	01 January	31 December	M			
Year	First Treatment Date	Date of Data Cutoff/Lock	Y			

If the imputation of an AE start date leads to a date prior to the date of first vaccination, and it is possible that the AE start date can be on or after date of first vaccination based on partial date information (e.g., occurred on the same month), it will be set to the date of first vaccination to be conservative. In the event the imputation of an end date leads to a date after the death date of a subject, the death date will replace the imputed date.

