## 3.5.3.4 Secondary Efficacy Analyses

## 3.5.3.4.1 PFS Based on Target Lesion(s)

PFS is defined as the time interval from first vaccination to objective tumor progression based on the mRECIST criteria or death, whichever occurs first. Subjects who do not have disease progression or have not died will be censored at the date when the last tumor assessment determines a lack of target tumor progression. The product-limit Kaplan-Meier curve will summarize PFS graphically. Median survival and 95% confidence intervals will be computed based on the product limit method (Greenwood's formula for the standard error estimate) overall and by subgroups defined in Section 3.3. Progression-free survival rates will be summarized by visit where scheduled tumor assessment is performed, along with their Wilson score confidence intervals.

Primary analyses of PFS will be based on the EAS. PFS rates will also be summarized for the FAS where subjects without post-treatment tumor assessment will be considered to have progressed. Median survival and 95% confidence interval will not be analyzed for the FAS, as these estimates will not differ from those for the EAS because censoring at time 0 is equivalent to excluding these subjects.

Additionally, PFS from current treatment versus PFS from previous treatment will be explored. The ratio of current treatment PFS in days / previous treatment PFS in days for each subject will be calculated. Summary statistics will be presented for EAS. It will also be summarized for EAS by current radiation treatment dose categories: <= median current radiation dose in Gray and > median current radiation dose in Gray. Highest dose of radiation treatment for each subject is used as defining the current radiation treatment dose categories. Subject's most recent previous treatment will be used for the derivation and calculation of PFS from previous treatment. Figures will also be generated to present the ratio by overall and by current treatment radiation dose categories.

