#### 3.5.5.2 Demographics and Baseline Characteristics Analyses

Demographics and baseline characteristics will be summarized based on the FAS. An additional summary table will be generated based on the EAS.

Age is recorded at the time of screening and will be presented using continuous statistics.

BMI will be calculated as:

 $BMI = weight (kg) / [height (m)]^2$ 

02 November, 2021

BRACHY-CHOR-001

Baseline disease characteristics will be summarized using continuous statistics or percentages and frequencies, as appropriate.

Disease duration at baseline in years will be calculated as:

If applicable, time from recurrence after a disease-free interval to first trial treatment in years will be calculated as

```
(Date of First Treatment - Date of Recurrence + 1) / 365.25
```

Note if either the initial diagnosis date or recurrence date are partial, they will be imputed based on the missing date rules in Section 3.4.1.

If dates are complete, duration of curative intervention and disease-free intervals will be calculated and will be included in subject-level listings only. Missing or partial dates will not be imputed.

Duration of curative intervention in months will be calculated as:

```
(End Date of Primary Curative Intervention - Start Date of Primary Curative Intervention + 1) / 30.4
```

Disease-free interval in months will be calculated as:

```
(Date of Recurrence - End Date of Primary Curative Intervention + 1) / 30.4
```

In addition, sites of metastasis will be included only in subject-level listings. Screening ECGs will also be listed.

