#### 3.5.6.2 Prior and Concomitant Medication

In this trial, all non-cancer treatment prior and concomitant medications taken in the 90 days prior to the screening visit will be captured. Prior medications are defined as those medications started prior to the date of first vaccination with trial product. Concomitant medications include those that are started prior to first vaccination and are ongoing at the time of first vaccination, or those that start after first vaccination. Medications can be classified as both prior and concomitant.

Other cancer therapies started after trial treatment (if allowed per protocol) will be captured on the concomitant medications page.

All prior and concomitant medications will be coded using the WHO Drug Dictionary B3 Global version March 2018 (or higher).

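### One date-imputation table serves adverse events and pre-trial cancer history alike, so a pre-trial date with missing year yields an impossible or misclassified value

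*SAP*

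**What the plan says.** SAP 3.4.1 gives its purpose as "it may be necessary to impute incomplete dates to correctly assign events to a period or to calculate durations". One table follows, with the scope "For prior and concomitant medications, AEs, and cancer history dates, the following rules will apply". Its rules are:

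- Day missing: a start goes to the first of the month, an end to the last.
- Month missing: a start goes to 1 January, an end to 31 December.
- Year missing: a start goes to "First Treatment Date", an end to "Date of Data Cutoff/Lock".

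Two clauses follow the table. One is limited to adverse events ("If the imputation of an AE start date leads to a date prior to the date of first vaccination") and can move the start up to first vaccination. The other replaces an imputed end date that falls after death by the death date. Neither keeps a pre-trial event before consent or first vaccination.

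Three later sections depend on these dates:

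- **3.5.5.2** applies the table by name: "initial diagnosis date or recurrence date are partial, they will be imputed based on the missing date rules in Section 3.4.1". The same section declines to impute for duration of curative intervention and disease-free interval. Section 3.5.5.1 runs disease duration from diagnosis to informed consent.
- **3.5.6.2** states: "Prior medications are defined as those medications started prior to the date of first vaccination with trial product". Concomitant means begun earlier and still in use at first vaccination, or begun after it.
- **3.5.3.4.1** plans a per-subject ratio of current to previous PFS and says the "most recent previous treatment will be used for the derivation and calculation of PFS from previous treatment". It gives neither the start and progression dates nor a missing-date rule.

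**The concern.** For an adverse event, moving an unknown start to first treatment is cautious, because the event is then counted as treatment-emergent. For a diagnosis, a recurrence or a prior therapy, the event is already known to precede the trial. The same rule then moves it to a date on which it cannot have happened. The missing-year end rule is worse, since it carries a finished therapy through to data cutoff.

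At stake are the baseline disease table, the split of medications into prior and concomitant, and possibly the exploratory PFS ratio. The SAP also treats neighbouring variables differently. In 3.5.5.2 a partial recurrence date is imputed for time from recurrence but not for the disease-free interval.

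**Working it through.** The documents give no figure on this point, so there is none to reproduce. The check applies the 3.4.1 rules by date arithmetic. First treatment is the first vaccination.

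**1. Disease duration, diagnosis year missing.** Diagnosis is set to first treatment. The gap from consent to first vaccination is not stated. I assume 0 to 28 days, guided by the 28-day baseline imaging window. The formula in 3.5.5.2 did not come through in the text I had, so both conventions are shown, with g the gap in days.

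| g (days) | (1 - g)/365.25 | -g/365.25 |
|---|---|---|
| 0 | +0.003 | 0 |
| 1 | 0 | -0.003 |
| 7 | -0.016 | -0.019 |
| 16 | -0.041 | -0.044 |
| 28 | -0.074 | -0.077 |

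Duration is zero or negative from g = 1 upward.

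**2. Disease duration, day or month missing.** The imputed diagnosis is never later than the true one, so duration is only lengthened. The most it can gain is 30/365.25 = 0.08 years (day) or 364/365.25 = 1.00 year (month).

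**3. Time from recurrence, year missing.** The SAP formula gives (0 + 1)/365.25 = 0.003 years, that is, 1 day. This uses the start-date column, although the SAP does not say which column a recurrence date takes. Under the end-date column, with the month missing in the year of first treatment, the result can be negative. For first treatment on 30 June it is (-184 + 1)/365.25 = -0.50 years.

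**4. Medications.** With start year missing, the start becomes the vaccination day. That is not before first vaccination, so the medication is not prior. It is neither begun earlier and ongoing nor begun after, so it is not concomitant. With end year missing, the end becomes data cutoff, so a past therapy appears to run during the trial. Protocol exclusion criterion 1 bars concurrent systemic cancer treatment, and inclusion criterion 8 requires at least 2 weeks since earlier treatment.

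**5. PFS ratio, conditional on 3.4.1 being applied.** Assumptions:

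- True previous PFS is 274 days. This is for scale only; 9 months is a median PFS in protocol Table 1.
- Current PFS is also 274 days, so the true ratio is 1.00.
- Progression is treated as an end date.
- First vaccination is 60 days after progression, and cutoff is 900 days after that.
- All 365 start days of a year are equally likely.

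Previous PFS = progression - start + 1.

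| Missing | Previous PFS (days) | Ratio |
|---|---|---|
| Start day | 274 to 304 | 0.90 to 1.00 |
| Start month | 274 to 638 | 0.43 to 1.00 |
| Both months | 365 or 730 | 0.75 or 0.38 |
| Start year only | -59 | 274/(-59) = -4.64 |
| End year only | 1234 | 0.22 |
| Both years | 900 + 1 = 901 | 274/901 = 0.30 |

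With both months missing, about 25% of start days give 365 and 75% give 730. The mean multiplier is 0.25 × 0.75 + 0.75 × 0.375 = 0.47. With one month missing, the mean multiplier is about 0.64.

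If progression took the start-date column with its month missing, previous PFS would be shortened instead. It would be zero or negative for 25% of start days (34% for a true value of 240 days, none for 365).

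To show leverage, suppose all 29 planned evaluable subjects have a ratio, 28 of them at 1.00 and one at -4.64. The mean is (28 - 4.64)/29 = 0.81.

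**The case against.** The strongest reply concerns the PFS ratio. Section 3.4.1 does not define cancer history dates. Prior chordoma therapy has its own section, 3.5.6.1, whose list names no progression date. Section 3.5.5.2 invokes the table for diagnosis and recurrence only. A reader might infer that the SAP commits the ratio to these rules and so to a known bias. The documents do not support that: 3.5.3.4.1 is silent, and the direction of the error depends on which column progression takes. This part of the objection stands, and leaves an undefined denominator with a conditional distortion.

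A reader might also infer that any partial diagnosis date gives zero or negative duration. It does not; the year must be missing. Section 3.5.5.2 speaks of partial dates, so using the year row there is itself a reading, though the heading of 3.4.1 covers missing dates as well and the table has a row for the year.

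Dividing 274 by the mean imputed value of 638 gives 0.43, which might be taken as the typical effect with both months missing. It is a ratio of means; no subject takes that value, and the mean multiplier is 0.47.

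Two mitigations are fair. Data are listed as captured, and imputed dates carry a flag, so affected values can be found. The no-imputation rule also protects two of the derived intervals. Neither corrects the summary tables.

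**Conclusion.** The point holds for the baseline and medication variables. For a pre-trial date with missing year, the stated rule gives a disease duration that is zero or negative when consent is at least one day before first vaccination, a time from recurrence of 1 day (start-date column), and a prior medication that fits neither class. A missing month overstates disease duration by up to about one year.

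For the PFS ratio the effect is conditional. If 3.4.1 is applied under the assumptions above with both months missing, the ratio is multiplied by 0.38 to 0.75, mean about 0.47. With only the start year missing it can be negative.

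The effect on any summary cannot be sized, because the number of partial dates is not given. Nothing in the documents shows that old therapy dates are the ones most often partial, and the ratio uses the most recent treatment. ORR, its test and the main PFS analysis do not use these dates. This should be corrected before the final analysis, but it does not threaten the trial's main conclusion.

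**What to change.** In SAP 3.4.1, limit the missing-year row to adverse events and on-trial medications. Then add:

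- For cancer-history and prior-therapy dates, do not impute when the year is missing; report the derived value as missing.
- Cap every other imputed pre-trial date so that it falls before consent or first vaccination, as the variable requires, and so that no end precedes its start. A mid-month rule would need the same check: a start of 20 March with an end known only as March would otherwise end on 15 March.
- Class a medication reported as prior with unknown start year as prior.
- In 3.5.3.4.1, state which start and progression dates define previous-treatment PFS. Leave out of the ratio any subject with a missing month or year at either end, and report how many.

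The cost is SAP wording and minor programming. A few subjects would lose a disease-duration or PFS-ratio value.
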